**Effect of methotrexate carried by a lipid nanoemulsion
on left ventricular remodeling after
ST-elevation myocardial infarction**

NCT 03516903

October 13, 2020.

Statistical Analysis Plan

Study design: Prospective, double-blind, parallel arm, proof of concept, randomized controlled trial.

Study casuistic: 50 patients presenting with acute anterior wall STEMI, after proper reperfusion therapy and in stable clinical condition. Patients will be randomly assigned 1:1 to methotrexate carried by a lipid nanoemulsion (ddMTX-LDE) or matching placebo.

1. Study Population

The main population analysis of interest will be the *per protocol population*, that means, all patients who have been randomized and completed the 3 months follow-up with an adequate cardiac MRI with complete measurements of LV diastolic and systolic volumes and LVEF, and who have received at least one dose of the study drug. In an attempt to minimize bias for not doing an ITT analysis, baseline characteristics will be compared between both randomized arms within ITT and per protocol populations. Additionally, sensitivity analysis will be done including only patients who received the complete planned study doses of the investigational product.

2. Primary Endpoint

The primary endpoint of the study will be LV end-diastolic volume (LVEDV) assessed by cardiac MRI at 3 months. Both groups will be compared with a Student's t test or Wilcoxon rank sum test, as appropriate. Besides that, an analysis of variance (ANOVA) for repeated measures will be performed as sensitivity analysis in order to assess the serial measurements of LVEDV at baseline and at 3 months between both groups of interest, as well as comparison between groups regarding the difference between baseline and 3 months (delta). Mean difference between groups will be reported with corresponding 95% CI. If the variable does not follow a normal distribution, an alternative approach to estimate 95% CI will be used, like bootstrapping with 1,000 repetitions.

3. Safety endpoints

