Both groups will be compared regarding the incidence of the following pre-specified adverse events of special interest: overall serious adverse events (SAE), as defined in the protocol; adverse events of special interest (AESI), namely, stomatitis, vomiting, diarrhea, cough with fever or dyspnea; and fatal or life threatening infections (defined as those ones needing vital organ support measurements, like mechanical ventilation or vasopressors, as a direct consequence of the infection, e.g., septic shock). In those outcomes, these variables will be compared as binary variables, with Chi square or exact test, as appropriate, with risk ratios (RR) and 95% CI reported according to Wald proportion tests.

Laboratory parameters will also be compared between groups, following same principles outlined for the primary endpoint. Parameters of interest will be: hemoglobin, white cell blood count, platelet count, liver transaminases (AST and ALT), total bilirubin, and creatinine. Since some of those tests are performed weekly, we will use a mixed linear model with study drug and week as fixed effect and patient as random effect. Least mean squares difference with corresponding 95% CI will be reported. Besides that, we also report percentage of patients with at least one change in security laboratory parameter as prespecified by study protocol.

4. Sample size calculation

Sample size was calculated considering an expected 20% decrease in LVEDV in the LDE-MTX group compared to placebo, based on cardiac MRI at 3 months. From a prior study (the METOCARD study^{1,2}), the expected mean LVEDV in the placebo arm is 197.6 mL with a common SD of 45.7 mL. For a two-tailed alpha of 5% and 80% power, we estimate our sample size as 21 patients per group. In order to account for eventual losses, we planned to enroll a total of 50 patients.

5. Interim analyses

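### The only main analysis population is restricted to MRI completers and section 3 names no safety set, so as written treated patients who die or leave before the MRI drop out of the safety comparisons

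*SAP*

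**What the plan says.** SAP section 1, under a heading that covers the whole study population, names one main analysis population, called per protocol. A patient must have been randomised, have received at least one dose, and have "completed the 3 months follow-up with an adequate cardiac MRI" giving complete LV volumes and LVEF. The section does not say for which endpoints this set applies.

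Two other sets appear in section 1:

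- The ITT population has a single stated use: "In an attempt to minimize bias for not doing an ITT analysis, baseline characteristics will be compared" between the arms in both populations.
- For the third set, a "sensitivity analysis will be done including only patients who received the complete planned study doses". It is defined by full dosing and is not said to bring back patients without the MRI.

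Section 3 gives the safety comparisons. It opens with "Both groups will be compared regarding the incidence of the following pre-specified adverse events of special interest: overall serious adverse events (SAE" and goes on to AESIs and "fatal or life threatening infections (defined as those ones needing vital organ support measurements". For laboratory values it says: "Since some of those tests are performed weekly, we will use a mixed linear model with study drug and week as fixed effect". It gives no denominator and no analysis set. It leaves the SAE definition and the laboratory change criteria to the protocol, but not the safety population.

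Section 4 supplies the sizes: "we estimate our sample size as 21 patients per group", and "In order to account for eventual losses, we planned to enroll a total of 50 patients".

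**The concern.** A patient harmed badly enough to die or leave before 3 months is the one a safety comparison most needs to keep. The MRI is taken after treatment, so requiring it selects patients on something that treatment may have affected, and the selection can differ between arms. A patient whose scan is merely technically inadequate would also lose all recorded adverse events.

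The stakes are raised by the trial's size and by its own safety rule. Section 5 says the two planned safety analyses could stop the study for any important imbalance, whatever the significance level. With about 25 patients per arm, the absence of a few events can hide or create such an imbalance.

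**Working it through.** **1. Which set applies to section 3?**

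| Set in section 1 | Stated use | Keeps a dosed patient who dies or leaves before the MRI? |
|---|---|---|
| Per protocol (dosed, 3 months completed, adequate MRI) | Main analysis, no endpoint limit | No |
| ITT | Baseline characteristics only | Yes, but not used for outcomes |
| Complete planned doses | Sensitivity analysis | Not said to |

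Section 3 names none of these. An analyst working from the SAP alone has one main set to apply, and it is the first row.

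**2. What that does to the listed outcomes.** A patient who dies before the 3-month MRI cannot meet the first row's conditions. The fatal part of the infection outcome is therefore empty for deaths before the MRI. Life-threatening infections in patients who do reach the MRI still count. The weekly laboratory values of early leavers would go too, although the planned mixed model can use incomplete series.

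**3. The plan's own sample size (context; not disputed).** Inputs from section 4: 20% reduction from 197.6 mL, SD 45.7 mL, two-sided alpha 5%, power 80%.

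- Difference: 0.20 × 197.6 = 39.52 mL.
- n per group = 2 × (1.960 + 0.842)² × 45.7² / 39.52² ≈ 21.0, which reproduces the stated 21. A t-based calculation gives 22.

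**4. Loss allowance.** 50 − 2 × 21 = 8 patients; 8/50 = 16%.

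**5. Bounds on incidence.** Let an arm have m dosed patients, L of them without the MRI, and k patients with an event among the m − L completers. The report shows k/(m − L). Among all dosed patients the incidence lies between k/m (none of the lost had the event) and (k + L)/m (all of them did). Assumptions: all 50 dosed, 25 per arm, losses at the planned level.

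| Losses in the arm | Reported | Lowest among all dosed | Highest among all dosed |
|---|---|---|---|
| 4 | 0/21 = 0% | 0/25 = 0% | 4/25 = 16% |
| 4 | 2/21 = 9.5% | 2/25 = 8% | 6/25 = 24% |
| 8 (all in this arm) | 0/17 = 0% | 0/25 = 0% | 8/25 = 32% |

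**6. How a difference between arms can vanish (invented counts).** Suppose SAEs occur in 7/25 on active and 3/25 on placebo: RR = 0.28/0.12 = 2.33. Let 4 patients per arm lack the MRI, all 4 with an SAE on active and none on placebo. The completers then show 3/21 against 3/21, RR = 1.00.

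**The case against.** The strongest reply is that this is an unstated denominator read in its worst way. The SAP nowhere assigns the MRI completers to safety. Section 1 speaks of a main population, not the only one. Its entry condition, complete LV volumes and LVEF, makes sense only for MRI endpoints, and its worry about not using ITT reads as a worry about efficacy. An author who lists fatal infections probably did not mean to exclude early deaths. Safety looks confined to patients who had already finished 3 months would largely defeat the purpose of the analyses in section 5. The protocol, which is not at hand, may define a safety set.

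Much of this stands as evidence of intent, and intent is the uncertain part. It does not repair the text: section 1's rule carries no endpoint limit and section 3 offers no alternative. A safety set in the protocol would still leave section 1 needing that limit.

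Three narrower objections also stand:

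- The 8 is a recruitment margin, not a cap; actual losses could be larger. Some of the lost might never have been dosed, and the trial may stop short of 50.
- The upper ends of the ranges assume that every lost patient had the event, which nothing in the SAP supports.
- The laboratory point rests on the same reading of section 1. Section 3's instruction to treat laboratory values like the primary endpoint adds nothing, because section 2 sets tests and intervals and names no population.

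**Conclusion.** The concern holds in its conditional form: if section 1 is followed as written, dosed patients without an adequate 3-month MRI are left out of safety, which conflicts with having a fatal-event outcome. At the planned loss level this affects up to 8 of 50 patients (16%), assuming all 50 are dosed. The ranges above show how little a completers-only incidence would then say about all treated patients. The SAP gives no event or loss rates by arm, so neither the size nor the direction of the actual bias can be worked out. This should be fixed. Confidence is moderate, because the authors may well have intended otherwise.

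**What to change.** In section 1, add a clause limiting the MRI-based per-protocol population to the MRI endpoints. In section 3, add a sentence stating that all adverse-event and laboratory safety analyses include every randomised patient who received at least one dose, regardless of MRI or completion of follow-up. The safety analyses in section 5 should refer to the same set.

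The cost is a few lines of text. No visits, tests or sample-size figures change. There is one small downside: patients who leave early contribute events only up to their last contact, so follow-up time by arm should be reported beside the incidences.

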The study had two pre-specified safety analysis (it was deemed to be stopped should any important imbalance, regardless of significance level, be found between safety outcomes). However, due to difficulty in enrolment after COVID-19 pandemic, a new unplanned efficacy interim analyses will be performed aiming to decide whether the study should be interrupted for futility or efficacy. For this third interim analysis, study will be stopped for efficacy if the experimental therapy is superior to the placebo group at a two-sided alpha of 0.05, regarding the primary endpoint, or if there is any difference favoring MTX for LVEF at an alpha = 0.05. Additionally, the study will be interrupted for futility if the conditional completion is < 30% for the primary endpoint and for LVEF.

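### The laboratory safety model reports one drug difference averaged over weeks with no baseline covariate, so it can understate an effect that builds up and is less precise than the data allow

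*SAP*

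**What the plan says.** SAP section 3 (Safety endpoints) lists seven laboratory parameters: hemoglobin, white cells, platelets, AST, ALT, total bilirubin and creatinine. They are to be compared "following same principles outlined for the primary endpoint". The next step is introduced by "Since some of those tests are performed weekly", and the model is then fixed as a "mixed linear model with study drug and week as fixed effect and patient as random effect". The output is one line: "Least mean squares difference with corresponding 95% CI will be reported".

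Three other statements bear on the point:

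- Section 3 also promises the "percentage of patients with at least one change in security laboratory parameter as prespecified by study protocol".
- Section 2 (Primary Endpoint), whose principles are invoked, includes among its sensitivity analyses a "comparison between groups regarding the difference between baseline and 3 months (delta)".
- Section 5 (Interim analyses) refers to two safety looks, with stopping "should any important imbalance, regardless of significance level, be found between safety outcomes".

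The SAP does not give the number of weekly measurements, the laboratory SDs, the within-patient correlation or an expected size of toxicity.

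**The concern.** With drug and week as main effects only, the model has one drug parameter, held equal in every week. Changes in blood counts, transaminases or creatinine under repeated exposure need not be equal from week to week. If the difference grows, the early weeks pull the reported figure down, and nothing in the planned output would show the growth even though the weekly data exist.

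The missing baseline covariate is a separate matter. It does not cause the averaging. It leaves stable differences between patients in the error of the drug contrast and leaves chance baseline imbalance uncorrected. With 21 to 25 patients per arm, that loss of precision is worth avoiding.

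At stake is whether the main comparative estimate of haematological, liver and renal safety is as informative as the collected data permit.

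**Working it through.** **The plan's own figure.** The only computable figure in the SAP is the sample size for LVEDV (section 4): "For a two-tailed alpha of 5% and 80% power, we estimate our sample size as 21 patients per group". The assumed difference is 0.20 × 197.6 = 39.52 mL with SD 45.7 mL, so d = 39.52/45.7 = 0.865. Then n = 2(1.960 + 0.842)²/0.865² ≈ 21.0, and the figure reproduces. It bears on the laboratory model only by supplying the number per arm.

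**Assumptions not in the SAP.** K = 6 post-baseline weekly values; n = 21 per arm; unit SD in each week; equal correlation ρ = 0.5 or 0.7 between any two visits, baseline included; complete data. D is the drug difference in the last week, in SDs.

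**Step 1: what the averaged difference keeps.** With balanced data the drug estimate is the mean of the weekly differences. For linear growth, the share of the last-week difference kept is the mean of k/K over k = 1 to K, which is (K+1)/(2K).

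- K = 6: 7/12 = 0.58. For K = 4, 8 and 12 the shares are 0.63, 0.56 and 0.54.
- Baseline entered as an outcome week with zero effect: exactly 0.50.
- Effect only in the last three of six weeks: 3/6 = 0.50, or 3/7 = 0.43 with baseline as a week.
- Early plateau: 0.77 to 0.87. Immediate constant effect: 1.0.

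**Step 2: precision with and without the baseline covariate.** The variance of a patient's mean over K weeks is V = ρ + (1−ρ)/K. Its covariance with baseline is ρ, so adjustment leaves V − ρ². The standard error of the drug difference is √(2V/n), or √(2(V − ρ²)/n) when adjusted.

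| ρ | V | V − ρ² | SE | SE adjusted | Narrower by |
|---|---|---|---|---|---|
| 0.5 | 0.583 | 0.333 | 0.236 | 0.178 | 24% |
| 0.7 | 0.750 | 0.260 | 0.267 | 0.157 | 41% |

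This narrowing does not depend on the effect profile.

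**Step 3: power, D = 0.8, linear growth.** The averaged difference is 0.8 × 0.583 = 0.467. Divided by the standard errors above, it gives 1.98 and 1.75 unadjusted, and 2.62 and 2.97 adjusted. Two-sided 5% noncentral-t power:

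| Analysis | ρ = 0.5 | ρ = 0.7 |
|---|---|---|
| Averaged, no baseline | 49% | 40% |
| Averaged, baseline covariate | 72% | 82% |
| Last week, no baseline | 72% | 72% |
| Last week, baseline covariate | 83% | 94% |

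If baseline enters as an outcome week, the first row falls to 39% and 31%.

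**Step 4: sensitivity to effect size.** By normal approximation, with 21 per arm, K = 6 or 12, ρ from 0.3 to 0.85, and baseline either entered as an outcome week or left out, power of the averaged unadjusted difference is 14–31% at D = 0.5, 28–65% at 0.8, 41–83% at 1.0 and 74–99% at 1.5.

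**Step 5: the patient-level summary.** The share of patients with at least one protocol-defined change does not average over weeks. If the arms were tested on it with 21 each, power at assumed rates would be 80% for 5% against 40% and 83% for 10% against 50%, but 31% for 5% against 20% and 36% for 10% against 30%.

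**The case against.** A reader might infer that cumulative toxicity will be cut to about half its size and mostly missed. The SAP does not support that. Half the size needs a near-linear or late build-up, and no profile or schedule is given. Whether an effect is missed depends on its size and on the correlation: in step 4, power runs from 14% to 99%. Setting the unadjusted average against a baseline-adjusted last-week contrast would also change two things at once. Step 3 shows that the baseline covariate alone recovers much of the loss, with no interaction in the model.

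Averaging also has merits. For a constant difference of 0.5 SD from week 1 with ρ = 0.5, the unadjusted average has 54% power and the baseline-adjusted last-week contrast 45%. A last-week contrast would also miss a transient mid-treatment change. This is why the average should stay.

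The SAP has other safeguards. The at-least-one-change percentage is not diluted over weeks, and the safety looks require no significance test. Both count, but only in part. The percentage depends on thresholds and detects modest rate differences poorly. Section 5 does not say which laboratory quantity the looks review. Neither alters the reported model estimate.

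Finally, the reference to the primary-endpoint principles may bring in a change-from-baseline comparison, so it would be too strong to say that baseline is plainly ignored. But in section 2 that comparison is a sensitivity analysis with a single follow-up time. Section 3 does not say which week a laboratory change would use, and the model sentence does not mention baseline. The handling is unclear.

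**Conclusion.** The point stands as a moderate weakness in specification. As written, the laboratory model is additive, gives one averaged difference and names no baseline covariate. It can understate an effect that builds up: 58% of the last-week size for linear growth over six weeks, 50% with baseline as an outcome week, and no dilution for an immediate constant effect. It also gives up precision: adjustment would narrow the interval by 24 to 41%, which at 0.8 SD in the last week moves power from 40–49% to 72–82%.

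These sizes rest on six weekly values, 21 per arm, equal correlation of 0.5 to 0.7 and complete data. Of these, only the 21 per arm comes from the SAP. The additive structure and the absence of a baseline term in the model sentence are read directly from section 3. The documents do not show that toxicity will be missed.

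**What to change.** Reword the model sentence in section 3. Use the post-baseline weeks as outcomes. Enter drug, week, drug-by-week and the baseline value of the parameter as fixed effects, with patient as random effect. Report the least-squares mean difference averaged over weeks and the difference at each week, all with 95% confidence intervals, and label the weekly ones descriptive. State explicitly that baseline enters as a covariate and not as an outcome week, so that the reference to the primary-endpoint principles no longer leaves this open.

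No new data are needed, and the averaged difference remains available. The cost is that weekly intervals are wider than the averaged one and there are more of them. If all seven parameters were measured in six weeks there would be 7 × 6 = 42 contrasts, of which about 42 × 0.05 = 2 would be expected to exclude zero by chance with no drug effect. Without multiplicity control, they should be read as a pattern over time and not as separate tests.

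### The unplanned interim allows an efficacy stop at an unadjusted 0.05 on LVEDV or on LVEF alone, so the 5% error rate the trial is sized on is not held

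*SAP*

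**What the plan says.** Section 2 names one primary endpoint: "The primary endpoint of the study will be LV end-diastolic volume (LVEDV) assessed by cardiac MRI at 3 months". Section 4 sizes the trial on that endpoint, "considering an expected 20% decrease in LVEDV in the LDE-MTX group compared to placebo", where "the expected mean LVEDV in the placebo arm is 197.6 mL with a common SD of 45.7 mL". It concludes: "For a two-tailed alpha of 5% and 80% power, we estimate our sample size as 21 patients per group". Enrolment was raised to 50 to cover losses.

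Section 5 describes two safety analyses and then a third, unplanned interim analysis, prompted by slow enrolment in the pandemic. Under its efficacy rule the "study will be stopped for efficacy if the experimental therapy is superior to the placebo group at a two-sided alpha of 0.05" on the primary endpoint, "or if there is any difference favoring MTX for LVEF at an alpha = 0.05". Futility requires a value below 30% on both LVEDV and LVEF.

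The SAP does not say how many patients or what share of the information the interim will use. It gives no spending function, no significance level for the final analysis if the trial continues, and no multiplicity rule for the second endpoint. LVEF otherwise appears only in section 1, as a measurement that the 3-month MRI must provide.

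**The concern.** The 5% in section 4 belongs to one test of one endpoint at one time. Section 5 allows efficacy to be declared on LVEDV at the interim or on LVEF at the interim. If neither crosses, LVEDV is tested at the end. The first two are each set at 0.05, and nothing lowers the third below the 0.05 of section 4. Each added opportunity raises the chance of a false claim.

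Three consequences follow:

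- A stop under this rule cannot be reported as p<0.05 for the trial.
- The effect estimate at such a stop is biased upwards, because the trial stops when the estimate happens to be high.
- LVEF alone can end the trial as a success while LVEDV is not significant, leaving the primary question unanswered.

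**Working it through.** **1. Reproduce the plan's sample size.** Inputs from section 4: difference 0.20 × 197.6 = 39.52 mL, SD 45.7 mL, two-sided alpha 0.05, power 80%.

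n per group = 2 × (1.960 + 0.842)² × 45.7² / 39.52² = 20.99, which rounds up to 21.

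This matches the SAP. A one-sided 5% test would give 17. The stated size is therefore that of a single two-sided 0.05 test, with no alpha set aside for an interim.

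**2. LVEDV alone, tested at 0.05 at both looks.** Let t be the information fraction at the interim. Under no effect, the interim and final statistics Z₁ and Z₂ are standard normal with correlation √t. The overall error is P(|Z₁| > 1.96 or |Z₂| > 1.96). The final level of 0.05 is carried over from section 4, since section 5 gives none.

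**3. Add the LVEF trigger.** Let ρ be the correlation between the interim LVEDV and LVEF statistics, both oriented so that positive favours MTX. The error is now the chance that any of the three statistics crosses 1.96 (2 million simulated trials per scenario). The SAP gives neither t nor ρ, so a range is shown.

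False findings favouring MTX (nominal 2.5%):

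| t | LVEDV only | with LVEF, ρ=0.5 | ρ=0.7 | ρ=0.9 |
|---|---|---|---|---|
| 0.5 | 4.2% | 6.1% | 5.7% | 5.0% |
| 0.7 | 3.8% | 5.7% | 5.3% | 4.6% |
| 0.8 | 3.5% | 5.5% | 5.1% | 4.4% |
| 0.9 | 3.2% | 5.2% | 4.8% | 4.1% |

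Crossings in either direction (nominal 5%):

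| t | LVEDV only | with LVEF, ρ=0.5 | ρ=0.7 | ρ=0.9 |
|---|---|---|---|---|
| 0.5 | 8.3% | 12.2% | 11.4% | 10.1% |
| 0.7 | 7.6% | 11.4% | 10.6% | 9.3% |
| 0.8 | 7.1% | 11.0% | 10.2% | 8.8% |
| 0.9 | 6.5% | 10.5% | 9.6% | 8.2% |

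These figures read the LVEF level as two-sided, although section 5 gives no sidedness for it. Reading it as one-sided 0.05 raises the favourable error with LVEF to between 5.9% and 9.0% over t from 0.5 to 0.9 and ρ from 0 to 0.9.

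**4. Interim rule on its own.** Suppose the trial is certain to end at this look, so that no final test exists. The chance that LVEDV or LVEF falsely favours MTX is still 4.5% at ρ=0.5, 4.2% at ρ=0.7 and 3.5% at ρ=0.9, against 2.5%. This result does not depend on t or on the final level.

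**5. Overestimation on stopping.** If the planned effect is true, Z₁ has mean θ = 2.80√t. Given Z₁ > 1.96, its mean is θ + φ(1.96 − θ)/[1 − Φ(1.96 − θ)]. Dividing by θ gives about 1.40 at t=0.5 (θ=1.98) and 1.24 at t=0.7 (θ=2.34).

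**6. Stopping on LVEF only.** The SAP plans no LVEF effect, so any figure is illustrative. At t=0.5 and ρ of 0.5 to 0.7:

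- If LVEF has a standardised effect as large as that planned for LVEDV, and LVEDV has half its planned effect, about 36 to 37% of trials stop on LVEF with LVEDV not significant.
- If both endpoints have the full effect, the figure is about 13 to 17%.

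**The case against.** The strongest objection is that the two-direction figures overstate the problem. Section 5 stops for efficacy only when MTX is better, so an interim crossing in the harmful direction triggers no efficacy claim. Counting favourable interim stops plus a two-sided final test, LVEDV alone gives about 4.2 + 2.5 = 6.7% at t=0.5 and 3.5 + 2.5 = 6.0% at t=0.8. With LVEF at ρ of 0.5 to 0.7, it is 8.2 to 8.6% and 7.6 to 8.0%. This is fair. The favourable-only figures are the closest match to the rule and should be read first. They still exceed 2.5% in every scenario tried.

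Other points:

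- **The final level is inferred.** Section 5 is silent, and 0.05 comes from section 4. This stands as a matter of wording, but the interim rule alone already exceeds the nominal level (step 4).
- **Timing and correlation are unknown.** Both endpoints come from the same MRI, so ρ could be high, and a late look reduces the inflation. At t=0.9 and ρ=0.9 the favourable error is still 4.1%.
- **The futility rule might offset the excess.** It is not stated to be binding. Treated as binding, with its criterion read as conditional power under the current trend, it leaves 3.0 to 3.7% for LVEDV alone and 3.9 to 6.1% for either endpoint.
- **The protocol may define LVEF as an endpoint.** It may, so LVEF's absence from the SAP's endpoint sections carries little weight. Secondary status would not justify a second 0.05 for stopping.
- **This is a small proof-of-concept trial.** That tempers the consequences, but the SAP itself commits to a two-tailed 5%.
- **The safety looks.** They carry no efficacy test, and no alpha is charged to them here.

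**Conclusion.** The concern holds. Followed as written, section 5 gives an error rate above the one in section 4 at every timing and correlation examined. At t from 0.5 to 0.9 and ρ from 0.5 to 0.9, the chance of a false finding favouring MTX is 4.1 to 6.1% against 2.5%. With LVEF left out altogether it is 3.2 to 4.2%. The size depends on the assumed t, ρ and final level of 0.05. The existence of the excess does not, because the LVEDV-or-LVEF rule exceeds its nominal level at the interim alone.

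This must be fixed, because the rule decides both whether the trial stops and what it may claim.

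**What to change.** Amend section 5 before anyone sees unblinded interim results:

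- Make LVEDV the only endpoint that can stop the trial for efficacy. Remove the LVEF trigger and report LVEF descriptively at the interim.
- Replace the interim 0.05 with a group-sequential boundary, and state the information fraction and the final level. Any of these would serve:

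| Boundary | t | Interim p | Final p |
|---|---|---|---|
| Haybittle-Peto | any | 0.001 | 0.05 |
| O'Brien-Fleming-type spending | 0.5 | 0.0031 | 0.0490 |
| O'Brien-Fleming-type spending | 0.7 | 0.0148 | 0.0455 |
| O'Brien-Fleming-type spending | 0.9 | 0.0363 | 0.0401 |
| Pocock | 0.5 | 0.0294 | 0.0294 |
| Pocock | 0.7 | 0.0324 | 0.0324 |
| Pocock | 0.9 | 0.0383 | 0.0383 |

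Haybittle-Peto gives an overall two-sided error of 5.02% at t=0.5 and 5.00% at t=0.8. If the sponsor wants LVEF kept as a trigger, it needs its own share of alpha. Bonferroni over the three tests gives 0.05/3 = 0.0167 each. That would restore the error rate, but an LVEF-only stop would still leave LVEDV unanswered.

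The cost is SAP wording and a lower chance of stopping early; no more patients are needed. At t=0.5 with the planned effect, the chance of an LVEDV stop is 1 − Φ(1.96 − 1.98) = 51% at 0.05 and 1 − Φ(3.29 − 1.98) = about 10% at 0.001. Under Haybittle-Peto the final test stays at 0.05, so overall power is essentially unchanged.
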